noninferiority study that enrolled patients scheduled for elective major open abdominal or orthopedic surgery assessed the proportion of patients who responded “good” or “excellent” at the 48-hour timepoint on the Patient Global Assessment (PGA48) of method of pain control. The results showed that 78.5% vs. 65.6% of patients achieved PGA48 “success” for SSTS vs. IV PCA morphine, respectively, demonstrating non-inferiority as well as statistical superiority for treatment effect. Patients using SSTS reported more rapid onset of analgesia and patient and nurse ease of care and satisfaction scores were higher than IV PCA morphine. Adverse events were similar between the 2 groups, and SSTS had fewer patients experiencing oxygen desaturations below 95% compared to IV PCA morphine. Future studies are needed to determine patient populations that benefit most from the SSTS, assess the added values versus intravenous patient-controlled analgesia, and determine the pharmacoeconomics of the system³.

More recently, a study by Cassavaugh K et al.⁵ analyzed data from a hospital comparing 140 DSUVIA-treated patients with 157 matched historical controls. DSUVIA was dosed either 30 minutes before the end of surgery for longer surgeries or just prior to induction for shorter surgeries. Patients were a combination of inpatient and outpatients (same-day surgery). The data shows an overall 56% decrease in PACU IV morphine milligram equivalents (mean MME \pm SE) opioid requirements compared to control group receiving typical IV opioids (8.1 ± 0.5 to 3.6 ± 0.4 ; $p < 0.001$). The PACU Phase 1 discharge time also was significantly decreased compared to the control group (80 ± 2 min vs 66 ± 2 min; $p < 0.001$). From a safety perspective, 3 patients out of 157 required naloxone in the PACU to reverse respiratory depression in the control group and no naloxone was required in the DSUVIA group. PACU time is estimated to cost between \$6-\$8 per minute, therefore the time saved more than pays for the drug and can increase efficiency and possibly caseload. The investigator’s conclusion is that DSUVIA is a high therapeutic index opioid that has an extended duration of action into the PACU period thereby either

avoiding opioids completely in the PACU in many patients (48.5% of patients in the DSUVIA group vs 16.6% of patients in the control group), or significantly decreasing the amount of IV opioids required in the PACU and therefore decreasing PACU discharge time.

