Follow up following discharge

Prescription opioid use

Outcomes:

Primary:

Mean postoperative pain scores (PACU)

Secondary:

Mean postoperative pain scores (inpatient)

opioid consumption (MMEs, PACU and inpatient)

Frequency of opioid rescue medications given

PACU LOS (min)

hospital LOS (days)

nausea, vomiting, constipation, respiratory events

sedation level (PACU)

quality of recovery (QoR 15)

utilization of prescription opioids following discharge

As shown above, the following secondary outcomes will also be collected in the Study cohort to obtain estimates that can be used to power future randomized controlled trials: sedation level, quality of recovery (QoR-15)⁸, patient satisfaction score (satisfaction with the level of pain control, 6-point scale⁴), and utilization of prescription opioids following discharge.

Safety assessments will include adverse events (AEs) and use of concomitant medications, periodic monitoring of vital signs (blood pressure, heart rate, and respiratory rate), and continuous monitoring of oxygen saturation in the PACU.

Detailed Clinical Protocol

Preoperative:

The surgeon will approach the patient and introduce the study and one of the investigators will explain the study to the patient. The surgeon will assess subject at their visit. At this visit, the surgeons will identify any patients that may benefit from Dsuvia. The information will be provided to one of the investigators. The investigator will subsequently review their eligibility and inclusion criteria. If the subject continues to meet all the criteria, the investigator will explain the study with the patient. Thereafter the patients will be provided the consent forms for their review and a 24/7 contact number for any questions regarding this study. All patient questions will be answered and informed consent will be obtained by one of the investigators who is a licensed physician listed on the protocol. The patient will be provided contact information. A co-investigator will be available to answer

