- If at any time the patient's NRS >3 after 20 min following an administration of either Dsuvia or fentanyl, the patient can receive a repeat dose of fentanyl until again eligible to receive Dsuvia.

Once the patient is transferred to the floor, both groups will receive the standard of care postoperative pain management orders (ie PO and IV prn analgesia for NRS > 3).

Patients who require additional doses of Dsuvia will be monitored for respiratory depression for at least one hour after the last administration of the drug dose.

Sample Size/Statistical analysis:

The primary outcome is nurse-collected mean pain scores. Assuming a within-group standard deviation in PACU NRS pain score of 2.5 points⁷, enrollment of 30 patients in the study group and inclusion of at least 80 patients in each retrospective control group will provide at least 80% power at a two sided alpha level of 0.025 (0.05/2 pair-wise comparisons) to detect a minimal clinically important difference of 2 points⁹ between the Study group and each of the retrospective groups using linear regression.

To account for any potential lack of comparability in baseline characteristics between patients in the Study and retrospective groups, all outcomes will be compared between the prospective group and each of the retrospective groups using doubly robust estimation incorporating both multivariable linear regression adjustment and inverse probability of treatment weights based on the propensity score¹⁰. Doubly robust estimation will allow for unbiased treatment effect estimates even if one of the two models (i.e., propensity score model or outcome model) is miss-specified. The multivariable linear regression models for the outcomes will adjust for the following covariates: age, sex, BMI, ASA class, surgical invasiveness tier, reoperation, history of anxiety, anxiolytic use, history of depression, and antidepressant use. Analytic weights will be based on the inverse of the propensity score, calculated via logistic regression as the probability of being in the Dsuvia group conditional upon the aforementioned covariates included in the multivariable outcome model.

Investigator Name/Institution:

[name], MS
Associate Professor of Anaesthesia
Director, Neuroanesthesia

Brigham and Women's Hospital
Harvard Medical School
Department of Anesthesiology, Perioperative and Pain Medicine
[name]
[name]
[contact]
Email: [contact]

Senior Project Manager:
[name]
Email: [contact]

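### A single ten-covariate weighted linear model is set for all outcomes; it cannot give a reliable comparison for rare yes/no events, and no standard-error method is named for any outcome

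*Combined protocol and SAP*

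**What the plan says.** The section Sample Size/Statistical analysis gives one method for everything: "all outcomes will be compared between the prospective group and each of the retrospective groups using doubly robust estimation". As described there, the method joins a linear outcome model to propensity-score weights. The next reference to the outcome model is again linear: "The multivariable linear regression models for the outcomes will adjust for the following covariates", followed by ten covariates. Logistic regression appears only as the way to estimate the propensity score. No binary, count or exact method is named, and no variance estimator.

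The Outcomes section lists several kinds of secondary variable. "nausea, vomiting, constipation, respiratory events" are yes/no events. "Frequency of opioid rescue medications given" is a count. MMEs and length of stay are non-negative amounts. Hypothesis 2 rests on these variables.

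The plan also states a safeguard: doubly robust estimates stay unbiased "even if one of the two models (i.e., propensity score model or outcome model) is miss-specified".

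**The concern.** A linear model for a yes/no outcome estimates a risk difference, which is defensible when the event is common and the model is small. Here there are 30 treated patients, ten covariates and weights. If an event is rare, one arm may have none. Fitted risks then fall below zero, and the standard error rests on a handful of patients. The respiratory comparison bears on the safety of an opioid, and its p-value could be decided by a software default.

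The missing variance method matters more widely. Weights estimated from ten covariates in 110 patients make ordinary standard errors too small, whatever the type of outcome.

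**Working it through.** **1. The plan's own figure.** Inputs from Sample Size/Statistical analysis: 30 v 80 patients, SD 2.5, difference 2, two-sided alpha 0.025.
- SE = 2.5 × √(1/30 + 1/80) = 0.535.
- Power = Φ(2/0.535 − 2.241) = Φ(1.495) = 93.3% (92.7% by noncentral t).

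The stated minimum of 80% is met. This is the unweighted planning calculation.

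**2. Rare events.** The Background gives one respiratory rate: 3 of 157 controls in a cited study needed naloxone, and none of 140 Dsuvia patients did. Taking 3/157 = 1.91% in both arms as an assumption:
- Expected events: 30 × 0.0191 = 0.57 and 80 × 0.0191 = 1.53.
- P(no event in 30) = (1 − 3/157)^30 = 0.56.
- P(no event in 110) = (1 − 3/157)^110 = 0.12.
- With 0/30 on Dsuvia, Fisher's exact test needs at least 13/80 (16%) control events to reach p ≤ 0.025. Its type I error at 1.9% per arm is 0.5%.

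The documents give no spine-surgery rates, so the range is:

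| Event rate | Expected events, 30 / 80 | P(none in 30) |
|---|---|---|
| 1.9% | 0.6 / 1.5 | 56% |
| 5% | 1.5 / 4.0 | 21% |
| 10% | 3 / 8 | 4% |
| 30% | 9 / 24 | <0.1% |

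**3. Simulation of the written analysis under no effect.** Ten covariates, logistic propensity score, inverse probability weights, weighted linear regression, 30 v 80, nominal 2.5%, 2,000 runs per row. Covariate distributions and imbalance are assumed, as are the count and stay distributions. PACU MME was set to the Background's control mean of 8.1, SD 6.3 and about 16% zeros. Simulation error at 2.5% is √(0.025 × 0.975/2000) = 0.35 points.

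| Outcome | Negative fitted values | Rejection: model-based | HC0 | HC3 |
|---|---|---|---|---|
| Event 1.9% | 33% | 3.3% | 1.1% | 0% |
| Event 5% | 27% | 7.7% | 7.0% | 1.3% |
| Event 10% | 19% | 8.5% | 7.7% | 3.5% |
| Event 30% | 6% | 10.5% | 8.2% | 3.1% |
| Pain score (NRS) | 0% | 10.4% | 8.3% | 2.5% |
| MME | 0.2% | 10.8% | 8.8% | 2.5% |
| Rescue count | 1.1% | 10.1% | 8.0% | 2.2% |
| Stay | 0% | 9.8% | 7.7% | 2.2% |

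The 1.9% row uses only the 1,775 runs with at least one event. A second simulation agreed: at 1.9%, about 30% of fitted risks lay outside 0–1 and rejection ran from 0.1% to 2.8%; for a normal outcome, rejection was 8% (model-based), 6% (HC0) and under 2% (HC3). In the first simulation the weights left an effective sample of about 18 of the 30 Dsuvia patients and 72 of the 80 controls.

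**4. Does the linear form harm MME, counts or stay?** SD of the estimated mean difference under no effect, linear v log-link (1,500 runs): MME 1.53 v 1.53; count 0.55 v 0.55; stay 0.52 v 0.50. Power with HC3, linear v log-link: 96% v 94% for MME at the cited reduction (8.1 to 3.6), and 36% v 29% for a 40% lower count. The linear estimates were essentially unbiased under the null.

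**5. MME power, mean test v rank test.** SDs implied by the Background's standard errors: 0.5 × √157 = 6.3 and 0.4 × √140 = 4.7. With those SDs, the cited means and the cited zero shares ("48.5% of patients in the DSUVIA group vs 16.6% of patients in the control group"), simulated unadjusted power at alpha 0.025 is 92–93% by t-test and 94% by rank test.

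**The case against.** The strongest defence is the plan's own: double robustness protects the estimate even when the outcome model is wrong. That stands in part. At 1.9% the simulated linear estimate averaged −0.001 under no effect, so bias is not the problem. But the protection then rests on a propensity model with 30/10 = 3 treated patients per covariate. It is a large-sample property of the point estimate, and it does not supply a valid standard error with two events.

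A second defence is that negative fitted risks do not in themselves spoil a group contrast, and that nausea, vomiting and constipation may be common. Both stand. The documents give no rates for these events, and at 30% a linear risk difference is workable.

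Three stronger readings are tempting, and the documents support none of them.
- A reader might infer that linear analysis of MME, rescue counts and stay is invalid or inefficient. Step 4 shows no bias under the null and no meaningful efficiency loss; heavier tails than assumed could change this.
- A reader might infer from the zero share that mean-based tests of "opioid consumption (MMEs, PACU and inpatient") lose substantial power. At the cited spread the gap is 1–2 points. A large gap (76% v 88%) appears only with SDs of 8.1 and 5.4, above those the Background implies.
- A reader might blame the linear form for the excess type I error. The pain score shows the same excess, so the cause is the weights and the choice of variance estimator.

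Sedation, QoR-15, satisfaction and post-discharge opioid use are described as collected in the study cohort to inform later trials, so they are not clearly group comparisons.

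**Conclusion.** The concern holds in two limited parts.

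First, for rare yes/no events the written method cannot give a reliable comparison. At an assumed 1.9%, about two events are expected in 110 patients, roughly 30% of fitted risks are impossible, and null rejection moves between about 0% and 3% with the unstated standard error. This rests on naloxone use as a stand-in for respiratory events. A broader definition would be commoner, and the problem eases as the rate rises towards 30%.

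Second, the unnamed variance method matters for nearly every comparison, the primary outcome included. Under assumed covariates, model-based or HC0 errors reject about 6% to 11% of true nulls against 2.5%, while HC3 is close to nominal for most outcomes. Only the model-form part is confined to secondary outcomes.

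**What to change.** Add a short table to Sample Size/Statistical analysis, before data are analysed, naming effect measure, model and standard error by outcome type:
- **Outcomes reported as mean differences** (pain scores, MME, rescue counts, stay): keep the weighted linear model. Gamma, two-part or rank methods are a preference; some change the quantity estimated.
- **Rare yes/no events** (for example, fewer than about 5 per group): counts and exact intervals, with no adjusted test. For 0/30 the exact 95% upper limit is 1 − 0.025^(1/30) = 11.6%, which shows how little 30 patients can say. A ten-covariate logistic model would also fail here.
- **Common yes/no events**: weighted logistic regression standardised to a marginal risk difference, penalised if events are few for ten covariates.
- **All comparisons**: HC3 errors, or a bootstrap that refits the propensity model in each resample.

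The cost is wording and modest programming, with no new patients or data. The downside is the loss of an adjusted test for rare events. With 30 Dsuvia patients, a threshold of 5 events corresponds to 5/30 = 17%, so moderately uncommon events would also be reported descriptively.

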2. The perioperative use of Dsuvia (sufentanil SL) will be associated with lower overall opioid consumption, lower frequency of rescue opioids, lower PACU and hospital length of stay, and fewer side effects of opioid use (i.e., nausea, vomiting, constipation, respiratory complications) than observed in two historical control groups of patients receiving remifentanil or sufentanil infusions without perioperative Dsuvia.

Methods:

The study design is an Observational Longitudinal (OL) study with historical controls. There will be 1 prospectively recruited study arm (patients receiving the study drug Dsuvia) and 2 historical control arms (one that received an intraoperative remifentanil infusion and the other that received an intraoperative sufentanil infusion, both without Dsuvia).

Inclusion criteria:

[figure not shown]
Patients undergoing spine surgery (1-3 levels) who are opioid-naïve (no opioid use 30 days prior to surgery), 18-75 years old, ASA physical status 1-3.

Exclusion criteria:

Microdiscectomy, chronic opioid users, significant respiratory depression, acute or severe bronchial asthma, chronic lung disease, known or suspected gastrointestinal obstruction including paralytic ileus, liver disease (defined as alkaline phosphatase (ALP) > 56, aspartate aminotransferase (AST) > 100), known allergy or hypersensitivity to sufentanil or its components, baseline dementia, serotonin syndrome, adrenal insufficiency, severe hypotension, increased intracranial pressure, brain tumors, head injury, impaired consciousness, malignant hyperthermia, ASA physical status > 3, age > 75, pregnant patients.

IV. STUDY SCHEMA:

Patients undergoing spine surgery (1 or more levels)

Dsuvia 30mcg SL

Intraoperative Phase

General endotracheal anesthesia (TIVA with propofol/sufentanil)

Standardized anesthetic technique (see protocol below)

Dsuvia x1 prior to emergence from anesthesia

Postoperative Phase

Pain scores (NRS) q15 min up to 2 hrs

Concomitant Medication use/opioid consumption

Dsuvia prn q1hr as 1st line (NRS >3); Fentanyl prn as 2nd line, or 1st

line if repeat Dsuvia cannot yet be given and NRS is >3 (see PACU schema below)

Up to 3 doses of Dsuvia may be administered in the PACU (each at least 1 hr apart)

Hospitalization Phase

Follow up during inpatient hospital stay

Concomitant Medication use/pain scores

Both arms: standard of care analgesia (PO and IV prn)

Quality of Recovery (QoR); patient satisfaction (study arm only)

Post-discharge Phase

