questions on a 24 hour basis. It will be explained to the patient that they will be permitted to withdraw from the study at any time for any reason until their day of surgery. On arrival at the preoperative area, the patient will be assigned a code by one of the investigators. Prior to premedication, all patients will be made familiar with the use of numeric rating scale (NRS): 0-10 (no pain to the worst pain imaginable). The baseline NRS score will be recorded. All routine standard practices for surgery, anesthesia, and perioperative care will be followed with the exception of the study intervention. All patients will be premedicated with midazolam (0.025-0.05 mg/kg)

Intraoperative Management:

The Study arm will receive general endotracheal anesthesia (GETA). Anesthesia induction will be achieved with propofol (1.5-2.5mg/kg), succinylcholine (1mg/kg), and Fentanyl (50-100 mcg) bolus. Anesthesia maintenance will consist of TIVA (total intravenous anesthesia) with continued infusions of propofol (80-200 mcg/kg/min) and sufentanil (0.2-0.3mcg/kg/hr). The study group will receive Dsuvia 30 mcg at surgery end, administered by the anesthesiologist, timed to occur prior to emergence from anesthesia, and after the patient is turned supine. Antiemetic prophylaxis will be administered (ondansetron) per standard practice. The patient will then be transferred to the PACU.

Postoperative Management:

Note that Dsuvia will be ordered as q1hr prn, meaning that repeat doses must be administered at least 1 hr apart (up to 3 doses can be administered in the PACU).

Postoperative pain scores will be recorded by the PACU nurse and the research assistant. This will be obtained by using NRS scale every 15 mins up to 2 hours.

In the PACU, patients will be ordered to receive Dsuvia 30 mcg q1 hr prn for breakthrough pain (for NRS > 3) as the 1st line analgesic, with fentanyl as the rescue analgesic if the patient is still experiencing pain (NRS >3). The following opioid administration schema will be used for pain management in the PACU:

- 1st line: Dsuvia SL 30mcg (NRS >3). 2nd line: Fentanyl 25-50mcg (NRS >3)
- If upon arrival to the PACU the patient is still experiencing pain with NRS >3 but cannot yet receive a repeat dose of Dsuvia (because of having received 1st dose in the OR less than 1 hour ago), then the patient can receive fentanyl 25-50mcg prn until eligible to receive Dsuvia.

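### Intraoperative co-treatment is specified for the study arm, not for the historical controls, and is in neither adjustment model, leaving a risk of bias of unknown direction

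*Combined protocol and SAP*

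**What the plan says.** All references are to the combined protocol and SAP.

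- **Study arm.** The Study Schema lists "Standardized anesthetic technique (see protocol below"). The Preoperative and Intraoperative Management sections give the content: midazolam premedication; induction with propofol, succinylcholine and a fentanyl bolus; TIVA with propofol and sufentanil, each within a stated rate range; Dsuvia at the end of surgery. For nausea, "Antiemetic prophylaxis will be administered (ondansetron) per standard practice". Postoperative Management adds a PACU ladder of Dsuvia first and fentanyl second.
- **Controls.** Methods describes the two historical groups as "one that received an intraoperative remifentanil infusion and the other that received an intraoperative sufentanil infusion, both without Dsuvia". Nothing is said about their hypnotic or volatile agent, induction opioid, adjunct analgesics, antiemetics or PACU analgesics.
- **Adjustment.** Sample Size/Statistical analysis aims the adjustment at baseline comparability. The outcome model covers "age, sex, BMI, ASA class, surgical invasiveness tier, reoperation, history of anxiety, anxiolytic use, history of depression, and antidepressant use". The propensity model is conditional on the same list. The two medication items stand next to the matching diagnoses and read as patient history.

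**The concern.** Anaesthetic and analgesic co-treatment acts on PACU pain, the primary outcome, and on PACU opioid use. Antiemetic prophylaxis acts on nausea and vomiting. A control patient may have had volatile maintenance, a different infusion dose, or adjuncts such as ketamine, methadone or local infiltration. The plan neither excludes such charts nor measures the difference.

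The plan relies on doubly robust estimation, which it says stays unbiased if one of the two models is wrong. That property needs one of the models to contain every confounder that matters. A factor absent from both lies outside it. More control charts would not help either, since bias does not shrink as the groups grow. At stake is whether a significant result, or a null one, can be attributed to Dsuvia.

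**Working it through.** **Inputs from Sample Size/Statistical analysis**
- Group sizes: "enrollment of 30 patients in the study group and inclusion of at least 80 patients in each retrospective control group".
- SD: "Assuming a within-group standard deviation in PACU NRS pain score of 2.5 points".
- Significance level: "two sided alpha level of 0.025 (0.05/2 pair-wise comparisons").
- Target difference: 2 NRS points, with power of at least 80%.

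**The plan's own figure**
- SE of the difference = 2.5 × √(1/30 + 1/80) = 0.535.
- 2 / 0.535 = 3.74. With 108 df (30 + 80 − 2) and critical t = 2.273, power is 92.7% (93.3% by normal approximation). The claim of at least 80% holds and is not in dispute.
- The difference detectable with 80% power under the same inputs is 1.65 points (normal approximation).

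**Size of the possible bias**

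The documents give neither the effect of a co-treatment nor how its use differs between arms. Both are assumptions here:
- effect of an adjunct on mean PACU NRS: 1 to 2 points;
- difference between arms in the share of patients receiving it: 10 to 40 percentage points.

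Bias = effect × difference in prevalence. The last column is the two-sided rejection probability when Dsuvia has no effect (noncentral t, 108 df, SE 0.535, nominal 2.5%).

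| Effect (NRS) | Prevalence gap | Bias (NRS) | Bias / SE | Rejection probability |
|---|---|---|---|---|
| 1 | 0.10 | 0.1 | 0.19 | 2.7% |
| 2 | 0.10 | 0.2 | 0.37 | 3.5% |
| 1 | 0.40 | 0.4 | 0.75 | 6.8% |
| 2 | 0.40 | 0.8 | 1.49 | 22.3% |

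The calculation is unweighted and ignores what weighting and covariates do to the variance.

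The bias can run the other way. The study regimen names no non-opioid analgesic, so controls may have had more of them. A bias of 0.8 against Dsuvia would make a true 2-point benefit look like 2 − 0.8 = 1.2 points, below the 1.65 detectable with 80% power.

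**The two contrasts differ**
- *Sufentanil control:* the maintenance opioid is the same type as in the study arm. If the rest of the technique matches or is adjusted for, this contrast can isolate Dsuvia.
- *Remifentanil control:* the infusion differs from the study arm for every patient. There is no overlap, so no covariate can separate infusion from Dsuvia.

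**The case against.** A reader might infer that co-treatment is fixed in the study arm and unrestricted in the controls, so that differences in care are credited to Dsuvia as a matter of fact. The documents do not support that reading.

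- The study-arm technique is given as ranges and prn orders. The Preoperative section says that, apart from the study intervention, routine practice applies, and the antiemetic follows standard practice. Much of the background care may therefore resemble that of the controls.
- The controls are restricted by infusion and by absence of Dsuvia, and one group shares the study arm's maintenance opioid.
- On the floor, both groups receive standard care. The contrast in care is confined to theatre and the PACU.
- Concomitant medication use is listed as collected, so some of the data may already be at hand.
- No passage shows that control care differed, or which arm a difference would favour.
- The size rests on assumed inputs. The upper adjunct effect of 2 points equals the plan's whole target difference, and with a 10-point prevalence gap the error rate barely moves.

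All of this stands, and it makes the point a risk rather than a demonstrated bias. It does not remove the gap. The routine-practice sentence concerns prospectively enrolled patients and does not make past charts match a written regimen. Collecting concomitant medication does not put it in a model.

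**Conclusion.** The point holds as an unaddressed risk of bias. Intraoperative co-treatment is specified for one arm, not used to select controls beyond the infusion, and absent from both models, so double robustness gives no protection. Under the assumed ranges (adjunct effect 1 to 2 points, prevalence gap 10 to 40 percentage points), the bias is 0.1 to 0.8 NRS points in either direction. The false-positive rate per comparison is then about 2.7% to 22% against a nominal 2.5%. At the low end this is negligible; at the high end it would undermine attribution to Dsuvia. The documents do not say where in that range the study lies. The power statement is unaffected. The plan should be changed before the control charts are extracted.

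**What to change.** 1. **Selection.** Restrict both control groups to charts with propofol TIVA and no volatile maintenance, by a rule set before any outcome is seen.
2. **Extraction.** In all groups, record surgery duration, total infusion dose, antiemetic prophylaxis, and non-opioid and other adjunct analgesics given before the end of surgery, including methadone, ketamine, regional block and local infiltration. Tabulate them by arm.
3. **Models.** For the sufentanil-control contrast, add surgery duration and pre-Dsuvia adjunct analgesic use (any/none) to both the outcome and propensity models. Add antiemetic prophylaxis for nausea and vomiting. Do not adjust for drugs given in the PACU: they follow treatment, and PACU opioid use is itself a secondary outcome.
4. **Interpretation.** Treat the sufentanil control as the contrast that can isolate Dsuvia. Report the remifentanil contrast as a comparison of whole regimens. State that PACU analgesia is protocolised only in the study arm and is part of the regimen being compared.

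The cost is more chart extraction, fewer eligible control charts (so more must be screened to reach 80 per group), and a few more model terms with only 30 treated patients. Patient care does not change.
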